Note that xx is the average of the observations of the associated covariate in the Non-Exposure Event and yy is the average of the observations of the associated covariates in the Exposure Event. The value for the covariates to estimate the relative change between events denoted by xy is the average difference between Exposure and Non-Exposure events.

For acetaldehyde in Model 2, all 3 timepoints will be used in the analysis and a repeated measures analysis will be used to model the effects over time. Due to the equally spaced observations, a toeplitz structure will be fitted to the covariance structure to allow for variance components to be estimated at each timepoint. Heatstick and alcohol consumption will be fitted as fixed effects and their interaction terms will be added to the model as well.

```
proc mixed data=data;
class event exposure time;
model change=baseline exposure cumu_alcohol cumu_heatsticks
cumu_alcohol*cumu_heatsticks /ddf=kr solution;
repeated time/type=toep subject=event;
estimate 'Non-exp 3rd hr' intercept 1 baseline xx exposure 1 0 cumu_alcohol xx
cumu_heatsticks 0 cumu_alcohol*cumu_heatsticks 0 /e cl alpha=.05;
estimate 'Exp 3hr hr' intercept 1 baseline yy exposure 0 1 cumu_alcohol yy
cumu heatsticks yy cumu alcohol*cumu heatsticks yy/e cl alpha=.05;
estimate 'Change in carbonyl 3hr hr' intercept 0 baseline xy exposure 1 -1
cumu_alcohol xy cumu_heatsticks xy cumu_alcohol*cumu_heatsticks xy/e cl
alpha=.05;
run;
```

Note that xx is the average of the observations of the associated covariate in the Non-Exposure Event and yy is the average of the observations of the associated covariates in the Exposure Event. The value for the covariates to estimate the relative change between event types denoted by xy is the average difference between Exposure and Non-Exposure events.

Model 3 will be similar to Model 1 but with cumulative Heatstick consumption replaced by cumulative food consumption. The estimates from this model will be calculated at the mean levels calculated for each event type.

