Due to the irregular nominal times of the carbonyls, food/beverages and HeatStick consumption collection as shown in Table 7, we will pro-rate the values of the covariates against the time of carbonyl collection. For example, during a Non-Exposure Event at the end of the 1st hour for the carbonyls taken at 1730 the corresponding value for food or alcoholic beverages will be the sum of the 1st hour plus half of the 2nd hour. Similarly for an Exposure event, for the 2nd hour carbonyl reading the corresponding observation for food/beverages will be the cumulative sum until 2.5 hours and Heatsticks consumption will be the sum up to the 2nd hour plus a quarter of the 3rd hour observation.

From this model we will estimate the cumulative effects of the covariates on carbonyls at the end of 3 hours and also estimate the average concentrations of carbonyls in air over 3 hours.

For each type of carbonyl, boxplots of observations at each timepoint will be plotted against time and grouped by Event in the same figure.

A sensitivity analysis will also be performed matching the endpoints by the nominal timepoints, this approach is more conservative as the cumulative effects of food/beverage or HeatStick consumption is lower than what it actually was during time of the carbonyls reading.

Table 7. Nominal Sampling Times of Food/Beverages, IAQ parameters (Carbonyls) and HeatSticks consumption during Exposure and Non-Exposure Events

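### SAP 14.2, Model 2: rows labelled as third-hour take averaged running totals, so read literally they give a mid-period acetaldehyde value, and one set of rows serves two targets

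*SAP*

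**What the plan says.** SAP 14.2 adds post-hoc models for carbonyls in air. Model 2 is the acetaldehyde model: "For acetaldehyde in Model 2, all 3 timepoints will be used in the analysis". Its covariates are running totals (`cumu_alcohol`, `cumu_heatsticks`) and their product: "Heatstick and alcohol consumption will be fitted as fixed effects and their interaction terms will be added to the model as well". Time appears in the CLASS and REPEATED statements but not in the MODEL statement.

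The first ESTIMATE row begins "estimate 'Non-exp 3rd hr' intercept 1 baseline xx exposure 1 0 cumu_alcohol xx" and ends "cumu_heatsticks 0 cumu_alcohol*cumu_heatsticks 0 /e cl alpha=.05". The Exposure row and the contrast row also carry third-hour labels. The placeholders are defined once for the whole model. For `xx`: "Note that xx is the average of the observations of the associated covariate in the Non-Exposure Event". `yy` is the same for Exposure Events, and `xy` "is the average difference between Exposure and Non-Exposure events". None of the three is restricted to a particular reading.

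After the pro-rating rule, the section states the target: "From this model we will estimate the cumulative effects of the covariates on carbonyls at the end of 3 hours". The same sentence adds a second one, the mean air concentration over the 3 hours.

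**The concern.** A running total rises through the evening, so its average over three readings lies below its value at the last one. Because the model has no fixed time term, only the covariate values can move a prediction to hour 3. If averages over all readings are inserted, a row labelled third-hour returns a mid-period prediction.

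The section also names two targets but gives one set of rows and one evaluation rule. Two programmers could fill in the placeholders differently, and the label would not show which quantity was reported. Section 14.2 was added to examine the source of the rise in air constituents, and Model 2 is the only model in Table 6 that contains both HeatSticks and alcohol. An attenuated cumulative contribution would therefore bear on the question that the analysis was written to answer.

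**Working it through.** The SAP gives no figure for this point, so there is nothing to reproduce. The check has two parts.

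**1. What the literal rule returns**

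Write A for cumulative alcohol and H for cumulative HeatSticks. Apart from the intercept, baseline and event type, the prediction at reading t is

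b_A·A(t) + b_H·H(t) + b_AH·A(t)·H(t).

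Baseline is one mean pre-event value per event, so averaging over readings does not alter it. Putting in the all-reading means of A, H and A·H gives exactly the mean of the three hourly predictions on the model scale. That corresponds to the second stated target, carried under the label of the first.

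The definition of `xx` and `yy` repeats the one used for Model 1. There, Table 6 specifies the HeatStick covariate as the cumulative value at the third hour, one per event, so averaging can only be over events and does no harm. Model 2 has three rows per event.

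**2. How far the averages lie below the hour-3 values**

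Inputs, in hours of consumption credited to each carbonyl reading:

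| Covariate | Reading 1 | Reading 2 | Reading 3 |
|---|---|---|---|
| Alcohol | 1.5 (SAP 14.2, Non-Exposure example) | 2.5 (SAP 14.2, Exposure example) | 3.5 (assumed) |
| HeatSticks | 1.25 (assumed) | 2.25 (SAP 14.2, Exposure example) | 3.25 (assumed) |

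The assumed entries extend the SAP's examples in 1-hour steps, because the contents of Table 7 are not available. The alcohol series joins examples from the two event types.

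Shortfall = 1 − (mean over readings) / (value at reading 3). With constant consumption:

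- HeatSticks: mean 2.25; 1 − 2.25/3.25 = 30.8%.
- Alcohol: mean 2.5; 1 − 2.5/3.5 = 28.6%.
- Interaction: the products are 1.875, 5.625 and 11.375, with mean 6.29. Using the mean of products, 1 − 6.29/11.375 = 44.7%. Using the product of means, 1 − (2.5 × 2.25)/11.375 = 50.5%.
- Nominal times 1, 2, 3 (the SAP's sensitivity analysis): 1 − 2/3 = 33.3% for each main effect.

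Varying the hourly consumption pattern:

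| Pattern (hours 1 to 4) | Alcohol | HeatSticks |
|---|---|---|
| 8:4:2:1 | 13.8% | 16.4% |
| 4:3:2:1 | 19.3% | 22.5% |
| constant | 28.6% | 30.8% |
| 1:2:3:4 | 39.6% | 41.7% |

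Over all patterns tried, the interaction shortfall runs from 25.9% to 64.8%.

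These are shortfalls in covariate values, and hence in each term's contribution on the model scale. As an illustration, take the log scale (stated under Model 1, not restated for Model 2) and a hypothetical hour-3 HeatStick ratio of 1.50 that comes from the main effect alone. The literal row would show exp(0.692 × ln 1.50) = 1.32. If the interaction carried half of the hour-3 HeatStick effect, the combined shortfall would be (30.8 + 44.7)/2 ≈ 38% to (30.8 + 50.5)/2 ≈ 41%.

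**Contrast row.** The Non-Exposure row codes exposure as `1 0` and the Exposure row as `0 1`. The contrast row's `1 -1` is therefore Non-Exposure minus Exposure. `xy` reads as Exposure minus Non-Exposure, and the text under Model 1 reports ratios of Exposure relative to Non-Exposure. The event-type and covariate parts of that row run in opposite directions.

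**The case against.** The strongest reply is that the text does not say which readings the average covers. The row labels and the stated target both point to hour 3, and a mean over events of hour-3 values satisfies the label, the definition and the target together. The code is a template with placeholders. This stands: a reader might infer that the rows are certainly evaluated at the wrong point, or that the end-of-3-hours effect is never computed, and the documents show neither. They do show an evaluation rule that, read literally for a three-reading model, conflicts with its label, and two targets with one set of rows.

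A reader might also infer that the HeatStick and alcohol effect is understated by about 30%. That figure fits only the two main-effect terms under constant consumption. It omits the interaction and rests partly on extrapolated hours.

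Nor do these rows divide the acetaldehyde rise between HeatSticks and alcohol. Each is a single combined prediction or contrast. Attribution would come from the fitted coefficients, which the `solution` option prints and which do not depend on `xx`, `yy` or `xy`.

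Finally, the analysis is post-hoc, touches no primary endpoint, and sits in a study with no formal hypotheses. Hour-by-hour carbonyl data are also reported, in boxplots and in Table 15.2.2.3.3. This limits the consequence but does not settle what the Model 2 rows mean.

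**Conclusion.** The point holds as a conflict between the evaluation rule, the row labels and the stated targets, conditional on the literal reading. On that reading, the third-hour rows give a mid-period prediction. Under constant consumption and 1-hour steps beyond the SAP's examples, the covariate values used are about 31% (HeatSticks), 29% (alcohol) and 45-50% (interaction) below their hour-3 values. The main-effect range is about 14% to 42% over the patterns tried.

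The averages are too low under every pattern, because each running total was highest at the third reading. Whether the contribution is understated depends on the net slopes being positive; with slopes of mixed sign the direction is open. In the Non-Exposure row HeatSticks and the interaction are set to 0, so only alcohol is affected. The contrast row has a separate sign inconsistency, so the shortfalls above do not describe its whole error. The correction should be made because it costs little and the result is scheduled for reporting in Table 15.2.2.7.1.

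**What to change.** In SAP 14.2, Model 2:

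1. For the third-hour rows, define `xx` and `yy` as means over events, within event type, of the cumulative values at the third carbonyl reading. Set the interaction coefficient to the mean of the hour-3 products. Keep HeatSticks and the interaction at 0 in the Non-Exposure row.
2. Define `xy` as the Exposure minus Non-Exposure difference of those values, and code exposure in the contrast row in the same direction.
3. Add separately labelled rows at the all-reading averages for the 3-hour average concentration, and state the scale of the Model 2 endpoint.

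The cost is SAP wording, revised ESTIMATE coefficients and one extra set of rows. No new data are needed and the fitted model does not change.

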**Table 6. Covariates for Analysis of HPHCs in air**

Model	Time Points Used	Endpoint	Covariates
1	Average	Acetaldehyde	Baseline, Event Type, Cumulative Heatstick Consumption at 3 rd Hour
1	Average	Acrolein	Baseline, Event Type, Cumulative Heatstick Consumption at 3 rd Hour
1	Average	Crotonaldehyde	Baseline, Event Type, Cumulative Heatstick Consumption at 3 rd Hour
1	Average	Formaldehyde	Baseline, Event Type, Cumulative Heatstick Consumption at 3 rd Hour
2	All timepoints	Acetaldehyde	Baseline, Event Type, Heatstick Consumption, Alcoholic Beverages Consumption, Heatstick and Alcoholic Beverages interaction
3	Average	Acrolein	Baseline, Event Type, Cumulative Food Consumption during event
3	Average	Crotonaldehyde	Baseline, Event Type, Cumulative Food Consumption during event

Model 1 in Table 6 above describes a basic model relating the average levels of carbonyls to HeatSticks consumption. In this model the dependent variable is the change from baseline of the average reading of the carbonyls. Note that the average reading is taken as the mean of all readings from the three suitcases that were used to collect the carbonyls data. Baseline is the mean reading of all pre-event readings that were taken during a specific event. The endpoint change from baseline will be log-transformed prior to analysis. Baseline, Event type (Exposure or Non-Exposure), cumulative Heatstick usage will be fitted as fixed effects. Estimates of the carbonyl readings at mean levels of the covariates will be calculated for each event type. The estimates will be exponentiated and presented on the original scale. In addition to the estimates at an event level, the relative change in the carbonyls between an Exposure and Non-Exposure Event will be estimated as well. These estimates also be exponentiated and presented as a ratio of geometric means of an Exposure Event relative to a Non-Exposure Event. An example of the SAS code for model 1 is as given below.

```
proc mixed data=data;
class event exposure;
model ch=baseline exposure cumu_heatsticks /ddfm=kr solution;
estimate 'Non-exp 3rd hr' intercept 1 baseline xx exposure 1 0 cumu_heatsticks 0
/e cl alpha=.05;
```

```
estimate 'Exp 3hr hr' intercept 1 baseline yy exposure 0 1 cumu_heatsticks yy/e
cl alpha=.05;
estimate 'Change in carbonyl 3hr hr' intercept 0 baseline xy exposure 1 -1
cumu_heatsticks xy /e cl alpha=.05;
run;
```

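### The hourly acetaldehyde model (SAP 14.2, Model 2) has no time effect in its mean, so an unrelated rise during the evening would be credited mostly to the alcohol slope

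*SAP*

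**What the plan says.** SAP 14.2 is a post-hoc analysis added to look for the source of the increases in air constituents. For acetaldehyde, Model 2 uses all three hourly readings, and the text says that "a repeated measures analysis will be used to model the effects over time".

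The mean model is "model change=baseline exposure cumu_alcohol cumu_heatsticks", continued by "cumu_alcohol*cumu_heatsticks /ddf=kr solution". Table 6 lists the same terms: "Baseline, Event Type, Heatstick Consumption, Alcoholic Beverages Consumption, Heatstick and Alcoholic Beverages interaction". Neither contains time. Time appears in the CLASS statement and in "repeated time/type=toep subject=event", where it shapes the covariance only.

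The consumption covariates are running totals matched to the carbonyl sampling times. For the second-hour reading at an Exposure Event, "the corresponding observation for food/beverages will be the cumulative sum until 2.5 hours". The HeatStick covariate for that reading is likewise a running total: hours one and two in full, with one quarter of hour three added. In the ESTIMATE statement for Non-Exposure Events, HeatSticks and the interaction are set to 0.

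On the covariance, the SAP says that "a toeplitz structure will be fitted to the covariance structure to allow for variance components to be estimated at each timepoint".

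**The concern.** A running total cannot fall from hour 1 to hour 3. In a Non-Exposure Event, baseline and event type are constant and HeatSticks are zero, so cumulative alcohol is the only term that can follow a change over the evening. In an Exposure Event, alcohol, HeatSticks and their product all follow it. A rise from occupancy, cooking or outdoor air has no term of its own, and Model 2 has no food term either.

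Section 14.2 reads the fitted terms as cumulative effects of the covariates on carbonyls. If ordinary drift is credited to alcohol, the report could name drinks as a source of acetaldehyde on evidence that only shows the clock moving.

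**Working it through.** **Nothing to reproduce.** The documents state no power, precision or expected slope for Model 2. The check is a reading of the code plus simulation.

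**Inputs from the documents.** Four Exposure and two Non-Exposure Events (SAP 12.6.2.1.1), three hourly readings, and the fixed effects above. If readings are averaged within event and hour, there are 6 × 3 = 18 event-hours. The planned mean has 6 parameters (intercept, baseline, event type, alcohol, HeatSticks, interaction). Hour as a class effect adds 2, giving 8.

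**Inputs assumed.** Consumption levels (for example 60 drinks and 40 sticks per hour), between-event SD 0.10 and within-event SD 0.08 on the log scale, and the variability of consumption, which was varied. True alcohol and HeatStick effects are zero, and the trend is shared by all events.

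**Step 1: share of the rise credited to alcohol.** Generalised least squares with a compound-symmetry covariance and a trend of 0.10 log units per hour:

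| Assumed CV of consumption | Share credited to alcohol, no hour term | SE of alcohol slope, with hour / without |
|---|---|---|
| 10% between events | 96% (mean) | 5.9 |
| 15% between events | 95-96% (mean) | 4.9 |
| 30% between events | 88% (mean) | 3.0 |
| 30% between events, 30% between hours | 87% (median; 63-112%) | 2.6 |
| 50% between events, 50% between hours | 74% (median; 42-106%) | 1.8 |

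A repeat at the 50% end gave an average near 70%. With hour in the model, the credited share is 0.

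**Step 2: the same question with REML and a Toeplitz covariance** (150 runs per setting; log SD 0.1-0.3 between events for alcohol and 0.2 for HeatSticks). Credited to alcohol in Non-Exposure Events:
- True rise 0.2 from hour 1 to hour 3: 0.16-0.19, that is 0.16/0.2 = 80% to 0.19/0.2 = 95%.
- True rise 0.4: 0.31-0.37, that is 0.31/0.4 = 78% to 0.37/0.4 = 93%.

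The joint test of the three consumption terms, all truly zero, rejected in 19-29% of runs with no trend, 75-85% with a rise of 0.2 and 97-100% with a rise of 0.4. With hour added, the rate was 36-44% whatever the trend. The denominator degrees of freedom were approximated rather than Kenward-Roger, so the levels should not be read literally. The point is that dependence on the trend disappears.

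**Step 3: HeatSticks.** In Step 2 the net HeatStick-plus-interaction share in Exposure Events was small: a median of 0.01-0.03 for a rise of 0.2 and 0.04-0.08 for a rise of 0.4. The separate parts were large and opposite: 0.15 to 0.18 against -0.15 to -0.19 for a rise of 0.2, and 0.19 to 0.33 against -0.18 to -0.28 for a rise of 0.4.

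**Step 4: the contrast between event types.** The SAP evaluates each estimate at the average covariate values of that event type. The model contains an event-type indicator. With compound symmetry, residuals then sum to zero within each event type, so the estimate equals the observed event-type mean. A shared trend of 0.10, 0.20, 0.30 adds (0.10 + 0.20 + 0.30)/3 = 0.20 to both types, and 0.20 - 0.20 = 0. Simulation agreed: 0.000 with and without hour, with an SE ratio of 1.00. Under Toeplitz the middle hour can be weighted differently, so the equality is approximate. It also assumes that the event-type and covariate coefficients in the third ESTIMATE statement run in the same direction, which the example code leaves open.

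**Step 5: covariance.** For three times, TYPE=TOEP has one common variance and one covariance for each of two lags. It does not estimate a variance at each timepoint.

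**The case against.** The strongest reply is that the bias needs an unrelated trend, and the documents show none. Protocol 7.3.8 starts sampling one hour after entry so that the atmosphere is homogeneous during collection. That stands as a condition on the point: it makes a trend less likely but does not establish a flat level.

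Hour adjustment is also not neutral. Because cumulative consumption is close to a function of time, hour effects can absorb a genuine alcohol or HeatStick effect common to all events. This stands, and it is why both fits should be reported rather than one replaced by the other.

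The analysis is post hoc and concerns one carbonyl. The boxplots over time and the carbonyl tables by time would show a trend to the reader. They do not adjust for it, however, and the nominal-time sensitivity analysis only changes how times are matched.

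Three stronger readings are tempting, and the documents do not support them:
- That Model 2 will name alcohol whatever happens. It would tend to do so only if acetaldehyde rises for other reasons.
- That the net HeatStick effect is inflated to the same degree. A shared trend goes mainly to alcohol, the only consumption term that rises in both event types.
- That the Exposure versus Non-Exposure ratio is biased. At event-type covariate means it is not.

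**Conclusion.** The point holds for the slopes. Given an unrelated rise shared by all events, Model 2 credits about 70-96% of it on average to alcohol for consumption CVs of 50% down to 15%. The direction follows from the model; the size rests on assumed inputs and falls as consumption becomes more variable. The separate HeatStick and interaction coefficients are unstable, although their net share is small. Any estimate evaluated at hour-3 covariate values inherits the slopes. That matters because the ESTIMATE labels refer to the third hour while the covariate values are defined as averages. The point bears on the interpretation of a post-hoc analysis, not on a primary endpoint. The Toeplitz remark is a wording error with no computed consequence.

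**What to change.** - Fit Model 2 also with hour (three levels) in the MODEL statement, and report the alcohol, HeatStick and interaction slopes with and without it.
- State in SAP 14.2 that the acetaldehyde rise will not be attributed to alcohol or HeatSticks unless the finding survives adjustment for hour. Otherwise, state that six events cannot separate consumption from time.
- Delete or correct the sentence claiming variance components at each timepoint. Moving to a heterogeneous Toeplitz structure is not recommended: it adds covariance parameters to 18 event-hours already carrying 8 mean parameters, and SAP 14.4 reports a convergence failure in another air model.

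The cost is one extra fit and a few sentences. The price in precision is real: the alcohol-slope standard error grows roughly 2 to 6 times (1.8 at a CV of 50%, 5.9 at 10%), so the adjusted fit may be inconclusive.

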12.6.2.1.1 Carbonyls

During each Exposure and Non-Exposure Event, there are 3 sampling cases that collects air for the assessment of carbonyls at 1 hour intervals. Each sampling case was placed at the same location during an Event.

The SAS procedure PROC MIXED will be used with the restricted maximum likelihood method for estimation of the parameters. The mixed model will have the carbonyl reading as dependent variable and the following covariates will be included in the model: Location, Event Number (Exposure Events 1-4 and Non-Exposure Event 1 and 2) and Event Type (Exposure and Non-Exposure Event). A repeated statement will be used to model repeated measures for the time variable.

The denominator degrees of freedom will be determined using the method of Kenward and Roger (1997). In case of non-convergence of the preferred model or memory space issues, the Kenward-Roger method will be replaced by Satterthwaite approximation.

The SAS code for the mixed model to be used is shown below:

```
Proc mixed data=_data_ method=reml;
Class location time event_type;
Model endpoint = location event type event num/ ddfm=kr;
Repeated time/subject=location(event num) type=cs;
Lsmeans event_type / diff alpha=0.05 cl;
Lsmeans location / diff alpha=0.05 cl;
Run;
```

The Geometric LS means and estimate of the ratio of geometric means between Exposure and Non-Exposure Events along with its 95% CI will be presented in tables for Formaldehyde, Acetaldehyde, Acrolein and Crotonaldehyde. The geometric LS means and ratio of geometric means together with their respective CIs are calculated by exponentiating the LSmeans and differences between exposures groups.

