14.2 Additional Analysis to Explore Effect of Heatstick Consumption, Alcoholic Beverages and Food Consumption on Concentrations of HPHCs in Air

During the internal review period of the End of Trial Report for study P1-PES-01-JP and following a request of [REDACTED] after presentation of the preliminary results to the [REDACTED] it was identified that we should further examine the source of the increases of concentrations of Harmful or Potentially Harmful Constituents (HPHCs) in indoor air during a restaurant setting where the Non-Exposure and Exposure events took place by looking at the relationship between HeatStick consumption and its impact on HPHC concentrations including the IAQ markers acetaldehyde, formaldehyde, crotonaldehyde and acrolein. The statistical analysis defined in SAP version 1 did not allow an interpretation of these results directly, as it only included descriptive statistics.

To further explore the impact of potential impact of other covariates that may affect the concentrations of these HPHCs in air, we will use a linear regression model to assess the effects of beverage and food consumption on acetaldehyde, acrolein, crotonaldehyde and formaldehyde in addition to Heatsticks consumption. For acetaldehyde, we use a mixed effects repeated measures model representation to model the cumulative effects of these covariates over time as the covariates were measured on an hourly basis. A summary of the covariates used in the models are listed in Table 6.

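### SAP 14.2 promises food and beverage effects on air carbonyls on top of HeatSticks, but Model 3 swaps HeatSticks for food and formaldehyde gets no food or beverage model, so neither source coefficient is adjusted for the other

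*SAP*

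**What the plan says.** SAP 14.2 is a post hoc section. It was added because "we should further examine the source of the increases of concentrations" of harmful constituents in the restaurant air. It sets out to use regression "to assess the effects of beverage and food consumption on acetaldehyde, acrolein, crotonaldehyde and formaldehyde in addition to Heatsticks consumption", and refers to Table 6 for the covariates.

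Table 6 and the text around it then define three models:

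- **Model 1** (all four carbonyls): "Baseline, Event Type, Cumulative Heatstick Consumption at 3 rd Hour".
- **Model 2** (acetaldehyde only): "Baseline, Event Type, Heatstick Consumption, Alcoholic Beverages Consumption, Heatstick and Alcoholic Beverages interaction".
- **Model 3** (acrolein and crotonaldehyde only): "Baseline, Event Type, Cumulative Food Consumption during event". The text confirms it: "Model 3 will be similar to Model 1 but with cumulative Heatstick consumption replaced by cumulative food consumption".

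Models 1 and 3 use one value per event, because "the average reading is taken as the mean of all readings from the three suitcases that were used to collect the carbonyls data". SAP 12.6.2.1.1 gives the number of events: "Event Number (Exposure Events 1-4 and Non-Exposure Event 1 and 2", which makes six. Model 3 estimates are computed at each event type's own covariate means.

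**The concern.** The sentence that opens the analysis and the models that carry it out do not match. A reader of the sentence expects, for each of the four carbonyls, a food or beverage effect adjusted for HeatSticks. For acrolein and crotonaldehyde, food is never in the same model as HeatSticks. For formaldehyde there is no food or beverage term at all.

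This matters because the section is about the source of the increases. If the evenings with more HeatSticks were also those with more food eaten, a model with food alone would show a food coefficient that partly belongs to HeatSticks. A model with HeatSticks alone would show the reverse. Either coefficient could be reported as evidence for a source when the data do not separate the two.

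**Working it through.** **Step 1. Promise against specification.** HS = HeatSticks; joint = in the same model as HS.

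| Carbonyl | HS | Food | Beverages |
|---|---|---|---|
| Acetaldehyde | Models 1, 2 | none | Model 2, joint (alcoholic) |
| Acrolein | Model 1 | Model 3, without HS | none |
| Crotonaldehyde | Model 1 | Model 3, without HS | none |
| Formaldehyde | Model 1 | none | none |

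Only acetaldehyde has a second source fitted together with HeatSticks. Formaldehyde is named in the sentence but has no second source in any model.

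**Step 2. Degrees of freedom.** Model 3 has 6 observations and 4 parameters (intercept, baseline, Event Type, food), which leaves 2 residual df and a t multiplier of 4.30. Adding HeatSticks while keeping Event Type leaves 1 df and a multiplier of 12.71. Putting HeatSticks in place of Event Type keeps 2 df.

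**Step 3. What Event Type absorbs.** No product use is allowed at Non-Exposure Events, so HeatStick use is 0 there. The Event Type term therefore takes up the average HeatStick load of the Exposure Events. With an intercept and Event Type in the model, residuals sum to zero within each event type. The fitted value at each type's own covariate means is then the observed mean on the model's scale, with or without HeatSticks. Only HeatStick variation among the four Exposure evenings is left to leak.

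**Step 4. Expected size of the leak.** Let b be the HeatStick effect per SD, r the food–HeatStick correlation across Exposure evenings, and the true food effect 0. Within event types, food varies on (4 − 1) + (2 − 1) = 4 df, and only the 3 Exposure df can carry HeatStick variation. If food varies equally at both event types:

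expected Model 3 food coefficient = r × b × 3/4

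The simulation used 8,000 runs per setting. Its assumptions are not in the documents: b = 1, mean HeatStick use 5 SD at Exposure Events, residual SD 0.5, equal mean food at the two event types.

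| r | 0.75 × r | Simulated median, share of b | Food significant at 0.05 |
|---|---|---|---|
| 0 | 0 | 0.01 | 5% |
| 0.3 | 0.225 | 0.23 | 5% |
| 0.5 | 0.375 | 0.37 | 7% |
| 0.8 | 0.60 | 0.60 | 12% |
| 0.95 | 0.71 | 0.74 | 18% |

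The Event Type coefficient stayed near 5.0, the full average HeatStick load, throughout. The significance rates depend on the assumed residual SD: at r = 0.7 the rate is about 10% with SD 0.5 and 6% with SD 2. At r = 0.5 the median 95% CI for food is 4.26 wide, so the bias is 0.37 / 4.26 ≈ 9% of the width.

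**Step 5. The reverse leak in Model 1.** HeatSticks vary only among Exposure evenings (3 of 3 df). If food is the true source, with effect c per SD, the Model 1 HeatStick coefficient is expected to be r × c, for example 0.5 × c at r = 0.5. There is no 3/4 dilution here.

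**Step 6. The two joint models.** With baseline, Event Type, food and HeatSticks, the median food coefficient is about 0 at every r. However, the CI at r = 0.5 widens from 4.26 to 8.06, on 1 df. With baseline, food and HeatSticks (no Event Type), the food bias is also 0 when HeatSticks are the only cause of the event-type difference, and the CI is narrower than Model 3's (2.3 against 4.3 at r = 0.5). If instead the event types differ for another reason, with no true HeatStick or food effect, then at r = 0.7 this model gives a HeatStick slope of 0.96 and a food coefficient of −0.50 (10% significant). Model 3 then gives food 0.00 and 4.5%.

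**The case against.** The strongest case against has four parts.

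- *The wording can be read otherwise.* Assessing food in addition to HeatSticks may mean models run alongside Model 1. Table 6 and the text agree on Model 3, so no analyst would be unsure what to fit. This is a fair reading, and it leaves formaldehyde as the one plain mismatch. Even so, the food coefficient remains unadjusted, and the reader should be told.
- *The mechanism is not documented.* One might suppose that food and HeatSticks both rise with attendance. But active users are set at 20% ± 5% of the available seats (96 in SAP Table 1), not of attendees, which weakens that link. No correlation is reported. Protocol 2.1.1 also says that nicotine and acetaldehyde were the only HPHCs detected in air after IQOS use. That is the sponsor's own evidence, but it fits a plan that models two sources jointly only for acetaldehyde. This part stands: the leak is a possibility, not a finding.
- *The remedy can do harm.* Replacing Event Type by HeatSticks credits any other difference between Exposure and Non-Exposure evenings to HeatSticks (Step 6). This stands, and rules the swap out as the main model.
- *The weight is low.* The analysis is post hoc, there are no formal hypotheses, and the primary endpoints are untouched. This stands.

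A reader might also infer that Model 3 hands HeatStick emissions as a whole to food, or that the design favours food as the explanation. The documents support neither. Event Type holds the average load, and Model 1 leaks the other way.

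**Conclusion.** The point holds as a gap between the stated analysis and the specified one, with a limited consequence. SAP 14.2, followed as written, gives no food or beverage result for formaldehyde and no mutually adjusted food and HeatStick effects for acrolein or crotonaldehyde.

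The possible misattribution in Model 3 is about three quarters of the correlation times the HeatStick effect per SD. That runs from nothing at correlation 0 to about 70% at 0.95, given equal food variation at both event types, a linear HeatStick effect and a true food effect of 0. A negative correlation would reverse its sign. With 2 residual df the test would seldom call it significant, so the risk lies more in how a point estimate is read than in false positives. The mean for each event type is unaffected. What cannot be supported is a statement about source from Model 1 or Model 3 alone.

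**What to change.** 1. Add formaldehyde to Model 3 in Table 6, and reword the opening sentence of 14.2 to state which of food and beverages is assessed for which carbonyl.
2. Keep Model 3 with Event Type. Label its food coefficient as not adjusted for HeatSticks, and Model 1's HeatStick coefficient as not adjusted for food.
3. For acrolein, crotonaldehyde and formaldehyde, add as a sensitivity analysis only a model with baseline, cumulative food and cumulative HeatSticks. HeatSticks (0 at Non-Exposure Events) take the place of Event Type, leaving 2 residual df. Note beside it that it credits any other Exposure/Non-Exposure difference to HeatSticks.
4. State that neither food nor HeatSticks will be named as the source unless the main and sensitivity models agree, and that six events separate the two only weakly.

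The cost is a few lines of SAS code and SAP text, using consumption data already recorded under SAP 8.4 and 8.5. The price is slightly more analysis work and a more cautious conclusion about source.
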